1.3 Rationale

1.3.1 Rationale for the Trial and Selected Subject Population

In our study, we will study a different PD 1 drug (Pembrolizumab, Merck) for advanced HCC. This drug has been approved for treatment of malignant melanoma and has shown antitumor activity in several other malignancies. We have experience with this drug in treating cancer patients here at Sylvester. Since check point inhibitors (CPI) such as tremelimumab and nivolumab have shown activity in HCC, it is reasonable to assess Pembrolizumab in advanced HCC patients.

1.3.2 Rationale for Dose Selection/ Regimen/ Modification

An open-label Phase I trial (Protocol 001) was being conducted to evaluate the safety and clinical activity of single agent MK-3475. The dose escalation portion of this trial evaluated three dose levels, 1 mg/kg, 3 mg/kg, and 10 mg/kg, administered every 2 weeks (Q2W) in subjects with advanced solid tumors. All three dose levels were well tolerated and no dose-limiting toxicities were observed. This first in human study of MK-3475 showed evidence of target engagement and objective evidence of tumor size reduction at all dose levels (1 mg/kg, 3 mg/kg and 10 mg/kg Q2W). No MTD has been identified to date. 10.0 mg/kg Q2W, was the highest dose tested in PN001. Recent data from other clinical studies

within the MK-3475 program has shown that a lower dose of MK-3475 and a less frequent schedule may be sufficient for target engagement and clinical activity.

PK data analysis of MK-3475 administered Q2W and Q3W showed slow systemic clearance, limited volume of distribution, and a long half-life (refer to IB). Pharmacodynamic data (IL-2 release assay) suggested that peripheral target engagement is durable (>21 days). This early PK and pharmacodynamic data provides scientific rationale for testing a Q2W and Q3W dosing schedule.

A population pharmacokinetic analysis has been performed using serum concentration time data from 476 patients. Within the resulting population PK model, clearance and volume parameters of MK-3475 were found to be dependent on body weight. The relationship between clearance and body weight, with an allometric exponent of 0.59, is within the range observed for other antibodies and would support both body weight normalized dosing or a fixed dose across all body weights. MK-3475 has been found to have a wide therapeutic range based on the melanoma indication. The differences in exposure for a 200 mg fixed dose regimen relative to a 2 mg/kg Q3W body weight based regimen are anticipated to remain well within the established exposure margins of 0.5 – 5.0 for MK-3475 in the melanoma indication. The exposure margins are based on the notion of similar efficacy and safety in melanoma at 10 mg/kg Q3W vs. the dose regimen of 2 mg/kg Q3W (i.e. 5-fold higher dose and exposure). The population PK evaluation revealed that there was no significant impact of tumor burden on exposure. In addition, exposure was similar between the NSCLC and melanoma indications. Therefore, there are no anticipated changes in exposure between different indication settings.

The choice of the 200 mg Q 3W as an appropriate dose is based on simulations performed using the population PK model of pembrolizumab showing that the fixed dose of 200 mg every 3 weeks will provide exposure that 1)are optimally consistent with those obtained with the 2 mg/kg dose every 3 weeks, 2) will maintain individual patient exposures in the exposure range established in melanoma as associated with maximal efficacy response and 3) will maintain individual patients exposure in the exposure range established in melanoma that are well tolerated and safe. A fixed dose regimen will simplify the dosing regimen to be more convenient for physicians and to reduce potential for dosing errors. A fixed dosing scheme will also reduce complexity in the logistical chain and reduce wastage.

1.4 Gender and Ethnicity

There are no limitations in terms of gender or ethnicity for eligibility.

1.5 Correlative Studies

If available, tumor tissue either at time of diagnosis or archived tumor may be stained for PD-L-1 expression. In tumors such as melanoma, PD-L-1 expression is associated with higher response rate to PD-1 or PD-L-1 agents but even patients with no PD-L-1

expression may respond to these agents. To our knowledge, no data exists for HCC and PD-1 agents or PD-L-1 agents. Obtaining tumor tissue for correlative studies is optional for the patient. We will assess PD-L-1 tumor expression with clinical outcome. This is exploratory and there is no formal statistical analysis planned.

Patients who agree may have blood drawn (up to 30 mL if feasible) to perform immunologic markers (such as phenotype for T and NK cell markers by flow cytometry). Patients with hepatitis B or C will have blood (7 ml) drawn to assess viral titer load. These blood samples will be performed at baseline, every 3 weeks while on drug treatment and at the time of tumor response or progression. The purpose is to determine if immunologic markers and/or viral titers change with treatment. This is exploratory and no formal statistical analysis is planned. A descriptive analysis will be done for hypothesis-generating purposes but a statistical analysis will not be done as there may not be enough tumor tissue and blood samples collected (to conduct a formal statistical analysis).

We will also analyze several representative cytokines associated with T cell activation and suppression in serum, tumor biopsy and PBMCs from patients with pretreatment of anti-PD-1 and every 9 weeks (2-3 times) after anti-PD-1 treatment. T cell proliferation and activation in response to T cell receptor (TCR) and CD28 signals require IL-2, IL-12, IFN- γ stimulation, but can be suppressed by immunosuppressive cytokines such as IL-10 and TGF- β . This is exploratory and no formal statistical analysis is planned. A descriptive analysis will be done for hypothesis-generating purposes but a statistical analysis will not be done as there may not be enough tumor tissue and blood samples collected (to conduct a formal statistical analysis).

2.0 OBJECTIVES

2.1 Primary Objectives

- To determine the disease control rate (CR, PR or SD) and response rate (CR and PR) of pembrolizumab in patients with advanced HCC.
- To determine the safety of pembrolizumab in HCC patients.

2.2 Secondary Objectives

- To determine the progression-free survival (PFS), overall survival (OS), and objective response rate (ORR) and duration of response (DOR)

2.3 Exploratory Objectives

- To assess HCC tumor specimens (if available) for PD-L-1 expression, and correlate with response to therapy.
- To assess immunologic markers (if serum, available) for response.

- To assess changes in hepatitis B and/or hepatitis C viral titer load with pembrolizumab treatment for HCC.

3.0 ENDPOINTS

3.1 Primary endpoints

- Disease control rate (DCR) will be calculated per RECIST 1.1, as the proportion of patients with best overall response of complete response (CR), partial response (PR) or stable disease (SD) that is maintained for at least 8 weeks.
- Treatment-related adverse events (AEs) including serious adverse events (SAEs). AEs will be assessed by and assigned severity using the National Cancer Institute Common Terminology Criteria for Adverse Events (NCI CTCAE), Version 4.03.

3.1.1 Evaluable:

- Evaluable for DCR: Eligible subjects who receive at least one dose of pembrolizumab, have measurable disease at baseline, and have at least one post-baseline disease response assessment.
- Evaluable for Safety: Eligible subjects who receive at least one dose of pembrolizumab.

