3.2 Secondary endpoints

- Progression-free survival (PFS) will be defined as the elapsed time from the first date of study treatment until documented disease progression (as per RECIST 1.1) or death from any cause, whichever is earlier. For patients who remain alive without progression, follow-up time will be censored at the date of last disease assessment (as per RECIST 1.1).
- Overall survival (OS) will be defined as the elapsed time from the first date of study treatment to death from any cause. For surviving patients, follow-up will be censored at the date of last contact (or last date known to be alive). Follow-up for OS will occur every 12 weeks (± 1 month) until death or withdrawal of consent from the study.
- Objective response rate (ORR) will be defined as the proportion of the patients with a confirmed complete or partial response (CR or PR), as per RECIST 1.1.
- Duration of Response (DoR) will be defined as the elapsed time from documented tumor response to documented disease progression.

- 3.2.1 Evaluable for PFS, OS, ORR and DOR: Eligible subjects who receive at least one dose of pembrolizumab, have measurable disease at baseline, and have at least one post-baseline disease response assessment.

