7.0 STUDY DESIGN

The study will be an open-label, single-institution, non-randomized, single-arm, Phase II study of pembrolizumab therapy in patients with advanced HCC. Patients will be treated in three-week cycles, with intravenous (IV) administration of pembrolizumab on day 1 of each 3-week cycle. Trial therapy will last until withdrawal of consent, disease progression and/or unacceptable toxicity, whichever occurs first.

Correlative studies investigating PD-L-1 expression in tumor tissue will be assessed with clinical outcome. Peripheral blood will also be drawn to perform immunologic markers and hepatitis B or C viral titers. This is to determine if viral titers change with treatment. These studies are included for all patients who consent to the correlative studies (See Appendix F). There is an additional consent for the correlative studies.

Up to 28 evaluable patients will be enrolled at Sylvester Comprehensive Cancer Center (SCCC). We expect to enroll 10-12 patients per year based on our institution's enrollment capacity. Expected time to complete total accrual is approximately 1.5 years. Expected time to study completion is 3 years from date open to enrollment to allow for survival data. An interim analysis is planned after 14 evaluable patients are assessed for DCR to determine whether to continue with an additional 14 more.

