16.3 Analysis Set

Patients who are study eligible and receive at least one dose of Pembrolizumab will be considered evaluable for efficacy and toxicity, and will comprise the main analysis set.

Any patient who is enrolled on study but does not receive study treatment will be excluded from all analyses. Any patient who receives study treatment but is later found to be ineligible (e.g. protocol violation) will be withdrawn from study but will be followed for response, toxicity, and survival. The experience of such patients will be characterized separately from that of evaluable patients. Reasons for all exclusions will be characterized, such as eligibility subsequently not confirmed, or failure to receive treatment.

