16.4 Patient Enrollment and Study Duration

We plan to enroll up to 35 patients, to ensure that we have a minimum of 28 patients who are evaluable for the primary efficacy endpoint for this study, disease control rate (DCR). We expect to enroll 10-12 patients per year based on our institution's enrollment capacity.

Accrual will be suspended after 14 evaluable patients (stage 1) in order to assess DCR in accordance with the two-stage design of this trial.

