The Kaplan-Meier method will be used to estimate progression-free and overall survival rates and corresponding median times, if attained. Point estimates with corresponding 95% confidence intervals based on Greenwood's variance and the log-log transform method will be given for the proportion of progression-free/surviving patients at selected times, such as 3, 6, 12, 18, and 24 months following the initiation of treatment, as well as for median times, if attained [41]. For purposes of these analyses, progression-free survival will be measured from start date of treatment to date of documented disease progression, or death from any cause, whichever occurs first. Patients who are alive and progression-free will be censored at their date of last documented progression-free status. Overall survival will be measured from start date of treatment to date of death from any cause. Patients who are alive will be censored at their date of last contact. To the extent possible with 28 patients, we will explore the effect of baseline characteristics on progression-free and overall survival using Cox regression [42]. The objective response rate (ORR) will be estimated by the percentage of patients and corresponding 95% confidence interval using the exact binomial method.

To the extent that biomarker data are available, we will summarize expression levels of PD-L- 1 in tumor tissue, and serum titers of hepatitis B and/ hepatitis C in patients with hepatitis B or C, respectively, using descriptive statistics. A descriptive analysis will be done for hypothesis-generating purposes but a statistical analysis will not be done as there may not be enough tumor tissue and blood samples collected (to conduct a formal statistical analysis).

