17.2.3 Early Stopping for Lack of Efficacy

The Simon two-stage design of this trial, described in Section 16.2, provides for a single interim analysis of the primary study endpoint, disease control rate (DCR).

After enrollment of the first 14 evaluable patients in stage 1, accrual will be suspended and a decision to terminate the study early or continue accrual will be made. DCR of this cohort of 14 evaluable patients from stage 1 will be determined as a best overall response of either a CR, PR, or SD (as detailed in section 14.5). If no more than 2 of the first 14 patients achieve DCR, the trial will stop and pembrolizumab will be considered ineffective, as this suggests that the DCR is no better than the null hypothesis rate of 18%. If DCR is achieved in 3 or more of the first 14 patients, the trial will continue to a second stage and enroll an additional 14 patients for a total evaluable number of 28 patients. The findings of interim analysis of DCR from the first 14 patients of stage 1 will be reported to the Sylvester DSMC.

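### Section 3 limits the efficacy sets to patients with a post-baseline assessment and Section 16.3 does not; as written, Section 3.2.1 drops deaths before the first assessment from OS and PFS, and the DCR denominator is left open.

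*Combined protocol and SAP*

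**What the plan says.** **Section 3, Endpoints.** Section 3.1.1 reads "Evaluable for DCR: Eligible subjects who receive at least one dose of pembrolizumab, have measurable disease at baseline, and have at least one post-baseline"; what must follow baseline is an assessment of disease response. Section 3.2.1: "Evaluable for PFS, OS, ORR and DOR: Eligible subjects who receive at least one dose of pembrolizumab, have measurable disease at baseline", followed by the same requirement of a post-baseline assessment.

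**Section 16.3, Analysis Set.** Patients who are eligible and receive at least one dose "will be considered evaluable for efficacy and toxicity, and will comprise the main analysis set". The reasons for exclusion that it names are ineligibility and not being treated. A missing assessment is not among them.

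**Endpoint definitions.** Section 3.2: "Overall survival (OS) will be defined as the elapsed time from the first date of study treatment to death from any cause". Section 16.5: "Overall survival will be measured from start date of treatment to date of death from any cause". Both sections define PFS as time to progression or death from any cause.

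**Counts for the Simon rule.** Section 7: "An interim analysis is planned after 14 evaluable patients are assessed for DCR". Section 17.2.3: "After enrollment of the first 14 evaluable patients in stage 1, accrual will be suspended". Section 16.4 allows up to 35 enrolled patients so that at least 28 are evaluable for DCR. None of the three cites a definition of evaluable.

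**Section 14.2** adds a third wording, for objective response: at least one cycle and disease re-evaluated, with progression before the end of cycle 1 also counted as evaluable.

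**The concern.** Measurable disease is already inclusion criterion 2, so the operative difference between Section 3 and Section 16.3 is the post-baseline assessment. Someone programming the analysis can follow either section and claim to follow the protocol.

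For OS and PFS the condition selects on the outcome. The first scheduled scan is at week 9 (±9 days). A patient who dies unscanned before then has an early event under both endpoint definitions, yet fails the entry condition of Section 3.2.1. Taking out the earliest events can only raise the curves.

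For DCR the choice of set decides who is in the denominator and who fills the 14 and 28 places. The rule turns on single patients: 2 against 3 of 14, and 8 against 9 of 28. A dosed patient with no assessment has not shown disease control. Whether that patient counts as a failure or is left out can change either decision.

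**Working it through.** **1. The plan's own design.** Inputs from Section 16.2: p0 = 0.18, p1 = 0.43, n1 = 14, stop if 2 or fewer, n = 28, success if 9 or more. With X1 ~ Bin(14, p) and X2 ~ Bin(14, p):

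- Early stop = P(X1 ≤ 2)
- Success = Σ over x = 3 to 14 of P(X1 = x) · P(X2 ≥ 9 − x)

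Results: early stop 0.526 and success 0.0495 at p = 0.18; early stop 0.024 and success 0.905 at p = 0.43. These agree with the stated 53%, 5%, 2% and 90%, so the sample size is not in question.

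**2. OS and PFS.** If a share d of dosed patients die before any assessment and are dropped, then at a time t after those deaths, with no earlier censoring, true survival S(t) is reported as S(t)/(1 − d). This exceeds S(t) for any d > 0. The documents do not give d, so the size cannot be computed. As an illustration only: with d assumed to be 5% and S = 72%, the 6-month OS that Section 1.1 cites for nivolumab, 0.72/0.95 = 75.8%. The same ratio applies to PFS, because those deaths are PFS events too.

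**3. DCR.** Let d now be the share of dosed patients never assessed, all scored as not having disease control. Then DCR(dosed) = (1 − d) · DCR(assessed). The documents do not give d for this trial. The only guide is the nivolumab trial described in Section 1.1, with 41 enrolled and 39 evaluable for response: 2/41 = 4.9%, reasons not given. I therefore take 5% as the main assumption and show 10% as a wider case.

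False-positive rate of the unchanged rule:

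| Meaning of 18% | Set counted | p under the null, d = 5% / 10% | Error, d = 5% | Error, d = 10% |
|---|---|---|---|---|
| All dosed | 3.1.1 (assessed) | 0.18/0.95 = 0.1895; 0.18/0.90 = 0.2000 | 6.5% | 8.7% |
| All dosed | 16.3 (dosed) | 0.18; 0.18 | 4.95% | 4.95% |
| Assessed | 3.1.1 (assessed) | 0.18; 0.18 | 4.95% | 4.95% |
| Assessed | 16.3 (dosed) | 0.18 × 0.95 = 0.171; 0.18 × 0.90 = 0.162 | 3.7% | 2.7% |

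In the first row, early stopping under the null falls from 52.6% to 48.8% (d = 5%) and 44.8% (d = 10%).

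Power on the 16.3 set:

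- If 43% is a rate among all dosed patients, it stays at 90.5%.
- If 43% is a rate among assessed patients, p = 0.43 × 0.95 = 0.4085 gives 86.1%, and p = 0.43 × 0.90 = 0.387 gives 80.5%.

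**The case against.** **Section 16 may already govern.** Section 16.3 stands in the statistical section and names the main analysis set, and Section 16.5 analyses OS and PFS with no assessment condition. On that view Section 3.2.1 is a stray sentence. This is a possible reading, but nothing in Section 16 sets Section 3 aside, and 3.2.1 names OS and PFS expressly. The contradiction needs an edit either way.

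**The unassessed group should be small.** Entry requires ECOG 0 or 1 and a life expectancy of at least 12 weeks. Section 12.3 requires imaging at the off-treatment visit, and Section 14.5.4 asks that progression be documented even after discontinuation. Most patients who deteriorate should therefore be assessed and counted as failures under either set. This stands. What remains is mainly unscanned deaths and withdrawals, and 10% is about double the one guide in the documents.

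**The null is itself imprecise.** Section 16.2 puts the DCR on standard chemotherapy at 15–20%. Moving the null from 18% to 18.9% or 20.0% stays within that range, and at a true 20% the rule succeeds 8.7% of the time whichever set is used. This is fair, and it limits the weight of the error figures. It does not settle which patients are counted.

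**Stronger readings.** A reader might infer that the trial's type I error exceeds 5%. The documents do not support that, because Section 16.2 does not say whether 18% is a rate among dosed or assessed patients. A reader might also infer that unassessed dosed patients will be dropped and replaced. No passage says so. The wording of Sections 7 and 16.4 leans towards 3.1.1, but 16.4 directly follows 16.3, and its evaluable can equally be the 16.3 term. Nor do the seven places between 28 and 35 imply a 20% unassessed share, since no breakdown is given.

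**Conclusion.** The conflict is in the current text and should be fixed.

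- **Firm:** Section 3.2.1, taken as written, excludes deaths before any assessment from OS and PFS. That contradicts Sections 3.2, 16.3 and 16.5. The direction of the bias is upward; its size is unknown. This part needs no assumption beyond a literal reading.
- **Conditional:** the DCR denominator and the counts of 14 and 28 are ambiguous. If 18% is an all-dosed rate and the 3.1.1 set is used, the error rises from 4.95% to about 6.5% at an assumed 5% unassessed (8.7% at 10%), with every unassessed patient scored as not controlled. If 18% is a rate among assessed patients, it is unchanged.

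The sample size and the decision rule reproduce and are not criticised.

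**What to change.** 1. **OS and PFS.** Delete the post-baseline-assessment condition from Section 3.2.1 for these two endpoints. Analyse all eligible dosed patients from first dose and count unscanned deaths as events. For PFS, censor living patients with no post-baseline assessment at the first-dose date; Section 3.2 censors at the last disease assessment and leaves them without a date.
2. **DCR and ORR.** Name one set, use it for the counts of 14 and 28, and state in Section 16.2 that 18% and 43% refer to it. I would choose the 16.3 set with unassessed patients scored as not having disease control. It agrees with the plan's own main analysis set and keeps the error at or below 4.95% on either meaning of 18%.
3. **Sensitivity analysis.** Report DCR on the other set.
4. **Alignment.** Bring Sections 3.1.1, 14.2, 16.4 and 17.2.3 into line. DOR stays among responders, who have been assessed by definition.

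**Cost.** Item 1 costs wording only. With the 16.3 set, the reported DCR can be somewhat lower. If 43% was meant for assessed patients, power must be restated as about 86% at 5% unassessed, or 81% at 10%. The opposite choice is defensible if both rates are shown to be rates among assessed patients; it then keeps 4.95% and 90.5%, but Section 16.3 would have to be changed to match.

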3.2 Secondary endpoints

- Progression-free survival (PFS) will be defined as the elapsed time from the first date of study treatment until documented disease progression (as per RECIST 1.1) or death from any cause, whichever is earlier. For patients who remain alive without progression, follow-up time will be censored at the date of last disease assessment (as per RECIST 1.1).
- Overall survival (OS) will be defined as the elapsed time from the first date of study treatment to death from any cause. For surviving patients, follow-up will be censored at the date of last contact (or last date known to be alive). Follow-up for OS will occur every 12 weeks (± 1 month) until death or withdrawal of consent from the study.
- Objective response rate (ORR) will be defined as the proportion of the patients with a confirmed complete or partial response (CR or PR), as per RECIST 1.1.
- Duration of Response (DoR) will be defined as the elapsed time from documented tumor response to documented disease progression.

- 3.2.1 Evaluable for PFS, OS, ORR and DOR: Eligible subjects who receive at least one dose of pembrolizumab, have measurable disease at baseline, and have at least one post-baseline disease response assessment.

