APPENDIX J: PREPARATION AND ADMINISTRATION/ RECONSTITUTION OF PEMBROLIZUMAB
(KEYTRUDA®) FOR INJECTION (LYOPHILIZED POWDER)*100

ABBREVIATIONS & DEFINITIONS

Term	Abbreviation	Definition
Disease Control Rate	DCR	The proportion of patients with a confirmed complete response, partial response or stable disease (CR, PR or SD), as per RECIST v1.1.
Duration of Response	DOR	The length of time from documentation of tumor response to documented disease progression.
Overall Response Rate	ORR	The proportion of patients with a confirmed complete or partial response (CR or PR), as per RECIST v1.1.
Overall Survival	OS	The length of time from the start of treatment for a disease, that patients diagnosed with the disease are still alive.
Progression-Free Survival	PFS	The length of time during and after the treatment of a disease that a patient lives with the disease but it does not get worse.

Reference: National Cancer Institute (NCI) Dictionary of Cancer Terms
<http://www.cancer.gov/dictionary>

PROTOCOL SYNOPSIS

Protocol Title	Phase II Study of Pembrolizumab (Keytruda®) in Advanced, Unresectable Hepatocellular Carcinoma (HCC)																																																																			
Targeted Patient Population	Adult subjects (age ≥18 years) with confirmed advanced hepatocellular carcinoma (HCC).																																																																			
Study Design	The study will be an open-label, single-institution, non-randomized, phase II study of pembrolizumab therapy in patients with advanced HCC. Patients will be treated in three-week cycles, with intravenous (IV) administration of pembrolizumab on day 1 of each 3-week cycle. An interim analysis is planned after 14 evaluable patients are assessed for DCR to determine whether to continue with an additional 14 more.																																																																			

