14.5.5 Duration of Response

Duration of Overall Response

The duration of overall response is measured from the time measurement criteria are met for CR or PR (whichever is first recorded) until the first date that recurrent or progressive disease is objectively documented (taking as reference for progressive disease the smallest measurements recorded since the treatment started).

The duration of overall CR is measured from the time measurement criteria are first met for CR until the first date that progressive disease is objectively documented.

Duration of Stable Disease

Stable disease is measured from the start of the treatment until the criteria for progression are met, taking as reference the smallest measurements recorded since the treatment started, including the baseline measurements.

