16.5 Statistical Analysis

Demographics and baseline disease and treatment characteristics will be summarized using descriptive statistics such as counts and percentages, mean, standard deviation, median and range, as appropriate. This will include age, sex, race/ethnicity, performance status, prior systemic therapy, laboratory parameters (bone marrow function, liver function, etc.), and disease characteristics such as site (visceral, non-visceral), Child-Pugh classification and stage.

The number of Pembrolizumab injections received and reasons for treatment discontinuation will be summarized descriptively. Safety data, including toxicities, reasons for withdrawal from study treatment and laboratory data will also be summarized descriptively. Toxicities will be tabulated by type, grade, duration and attribution to treatment. A patient-level summary by worst grade toxicity will be included.

Efficacy analysis will include the primary study endpoint disease control rate (DCR), as well as the secondary endpoints, which include objective response rate (CR+PR), progression-free survival and overall survival. Disease control rate and overall response rate will be estimated by the percentage of patients achieving these criteria and the corresponding 95% confidence interval using the exact binomial method [40].

In addition, we will report median and range for the time to onset and duration of response for patients who achieve CR or PR. For patients whose best response is SD, we will report the median and range of SD duration.

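### Duration of response and duration of stable disease end only at documented progression, so a death without documented progression, which is a PFS event, gives them no end date

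*Combined protocol and SAP*

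**What the plan says.** **Duration of response (DoR).** The combined protocol and SAP defines it three times, each time without mentioning death:

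- Abbreviations & Definitions: "The length of time from documentation of tumor response to documented disease progression".
- Section 3.2: "Duration of Response (DoR) will be defined as the elapsed time from documented tumor response to documented disease progression".
- Section 14.5.5: it runs "until the first date that recurrent or progressive disease is objectively documented". Duration of complete response, in the same section, also ends at documented progression.

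**Duration of stable disease.** Section 14.5.5: "Stable disease is measured from the start of the treatment until the criteria for progression are met". Death is again not mentioned.

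**PFS.** Section 3.2 runs it "until documented disease progression (as per RECIST 1.1) or death from any cause, whichever is earlier". Section 14.8 has the same content, and 16.5 repeats it: "progression-free survival will be measured from start date of treatment to date of documented disease progression, or death from any cause, whichever occurs first". All three also give a censoring date for patients alive without progression.

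**Planned summaries.** Section 16.5 promises a median and range for DoR in patients with CR or PR. For stable disease: "For patients whose best response is SD, we will report the median and range of SD duration". It names no event rule, censoring rule or estimator for either. Kaplan-Meier is assigned to PFS and OS only.

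**The concern.** A patient in response or with stable disease who dies before a scan shows progression has reached an observed, dated, terminal event. PFS counts it. DoR and SD duration, as written, do not, and no other section says what to do with that patient. The analyst must therefore choose between leaving the patient out, treating the response or stability as still running, and counting the death despite the definition. That choice would be made after the data are seen.

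The case can arise in this trial. Eligibility allows a Child-Pugh score of 7, which Appendix G places in class B. Scans are 9 weeks apart. The SAE rules in 12.2 provide for deaths from causes other than progression. After treatment, follow-up may be by telephone on survival and later therapy (12.5), and the calendar in 12.6 marks no imaging in the follow-up column. A death may then be known when a progression is not.

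DoR is a named secondary endpoint; SD duration is a descriptive summary only. At stake is how those two results read, and whether they can be set beside PFS for the same patients.

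**Working it through.** **1. The plan's own figures.** The documents state no figure for DoR or SD duration, so there is none to reproduce. The two-stage design in 16.2 (14 then 28 patients; stop at 2 or fewer of 14; success at 9 or more of 28) reproduces by exact binomial calculation:

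- type I error 0.0495 at a disease control rate of 18% (stated level 5%);
- power 0.905 at 43% (stated 90%);
- early stopping 0.526 and 0.024 (stated 53% and 2%).

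None of these uses DoR or SD duration.

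**2. Set-up for the size.** Let λp be the hazard of documented progression and λd the hazard of death without it, constant and independent. Let f = λd/(λp+λd) be the share of first events that are such deaths. The values f = 10%, 20% and 30% are assumptions.

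**3. Deaths counted as events.** Median = ln2/(λp+λd).

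**4. Deaths censored in a Kaplan-Meier type estimate.** Median = ln2/λp. The ratio to step 3 is (λp+λd)/λp = 1/(1-f):

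- f = 10%: 1/0.9 = 1.11, or 11% longer;
- f = 20%: 1/0.8 = 1.25, or 25% longer;
- f = 30%: 1/0.7 = 1.43, or 43% longer.

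For an assumed true median of 8 months this gives 8.9, 10.0 and 11.4 months. For SD duration the factor overstates the effect. The clock starts at treatment, and SD must be met at least once at 8 weeks or later (14.5.4), so only the time after qualification is stretched. With qualifying time t0 and median remaining time m, the ratio is (t0 + m/(1-f))/(t0 + m), which is below 1/(1-f).

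**5. Patients who die are dropped.** With constant independent hazards, the time to the first event does not depend on which event it is. Among patients whose first event is progression, the median is still ln2/(λp+λd), so the population median does not change. What remains is a small-sample effect. The expected sample median of n exponential times, in units of their mean, is 0.783 for n = 6 or 5, 0.833 for n = 4 or 3, and 1 for n = 2 or 1. Averaging over the number left from six responders (binomial, retention 1-f) gives about 0.789, 0.803 and 0.824. Against 0.783, that is a rise of about 1%, 3% and 5%.

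**6. Time to last scan or to death entered in a plain median.** Each such value equals the time to death or is shorter, so the median cannot exceed the one obtained by counting death.

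**7. How many patients.** Section 1.1 cites 2 CR and 7 PR in 39 evaluable patients on nivolumab. Then 28 × 9/39 = 6.46, or about 6 responders. Patients with disease control number 9 at the success threshold, or 0.43 × 28 = 12.04 at the alternative. If all reach a first event, those with no defined end date number 0.9 to 2.7 (of 9) or 1.2 to 3.6 (of 12) for f from 10% to 30%.

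**The case against.** The strongest objection is to direction and size. A reader might infer that the plan makes control look 11% to 43% longer. The documents do not support that. The figure needs deaths to be censored in a Kaplan-Meier type estimate, and 16.5 reserves Kaplan-Meier for PFS and OS. The other handlings in the working leave the population median unchanged or give no lengthening. This stands: lengthening is one possible outcome, not the general consequence.

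A reader might also infer that such deaths are common here. No section gives a rate. Entry requires ECOG 0 or 1, bilirubin under 2 mg/dl and a life expectancy of at least 12 weeks. Cirrhosis is required by only one of the three diagnostic routes. Section 14.5.4 asks that objective progression be pursued even after treatment stops for symptomatic deterioration. This too stands: f is an assumption, and the relevant patients are those with disease control, not all enrolled.

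Finally, DoR and PFS are separate endpoints, the DoR definitions agree in substance, and a progression-only duration is a possible choice. So a reader who calls this a contradiction goes too far. But a progression-only definition still needs a rule for patients who die first, and none is given. It cannot be assumed that death is meant to count: where the plan intends that, it says so, as it does for PFS in the same list in 3.2.

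**Conclusion.** The gap is real and small. DoR and SD duration have no end date for a patient who dies without documented progression, although that death ends PFS, and 16.5 does not say how the patient enters the promised medians and ranges.

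The size depends on a choice that the plan leaves open. Censoring in a Kaplan-Meier type estimate lengthens the DoR median by 11%, 25% or 43% for an assumed f of 10%, 20% or 30%, with constant independent hazards. Dropping the patients leaves the population median unchanged on the same assumption, but with about 6 responders the loss of one or two can change the reported median and range.

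A reader might take this as a threat to the trial's main conclusion. It is not: the disease control test, sample size and stopping rules use neither duration.

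**What to change.** - **Abbreviations, 3.2 and 14.5.5:** end DoR at documented progression or death from any cause, whichever comes first, counted from the first documented response. End SD duration at the same events, counted from the start of treatment.
- **16.5:** apply to both durations the event and censoring rule already written there for PFS, and estimate both medians by Kaplan-Meier. This also gives a censoring date to responses and stable disease still ongoing, which a plain median and range cannot handle.

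The cost is wording only. Dates of death and of last disease assessment are already needed for PFS and OS, so no new data are required. The downside is that reported durations may be somewhat shorter than if such deaths were censored. With about 6 responders the Kaplan-Meier median will be imprecise and may not be reached. The change should be made before the durations are analysed.
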